6. DOSING DELAYS/DOSE MODIFICATIONS

Every effort should be made to administer investigational products using the planned dose and schedule.

Dose modifications may occur in one of two ways during study conduct:

- Within a cycle, dosing may be interrupted until adequate recovery from toxicities;
- Next cycle administration may be delayed due to persisting toxicity when a new cycle is due to commence.

Patients whose treatment is delayed due to adverse events should be evaluated at intervals of one week or less until adequate recovery has been documented or no further improvement is expected. No dose reductions are allowed for avelumab, utomilumab, PF-04518600, or rituximab. Intra-patient dose escalation is not allowed for any of the study drugs at any time.

Any suspected immune-related adverse event should be managed according to the Management of Immune Related Adverse Events (irAEs) guidance (see Table 2).

The same irAEs management guidelines will apply to utomilumab, avelumab and PF-04518600. In addition, in the event of an irAE, dosing with rituximab should continue per protocol if

applicable for the current cycle, but may be interrupted for the same duration as utomilumab, avelumab, and/or PF-04518600, or for longer at the discretion of the Investigator, following prior discussion with the Principal investigator.

In the event of significant toxicity; dosing may be delayed and/or reduced as outlined below. In the event of multiple toxicities, dose modifications should be based on the worst observed toxicity. Patients must be instructed to notify Investigators at the first occurrence of any adverse symptom/s.

All treatment modification recommendations must be followed unless previously discussed with and agreed by the Principal investigator. All dose modifications/adjustments must be clearly documented in the patient's notes and in the CRF.

6.1 Special Precautions for Avelumab Administration

As with all monoclonal antibody therapies, there is a risk of allergic reaction including anaphylactic shock.

In order to mitigate the risk of avelumab related infusion-related reactions, a pre-medication regimen comprising 25 to 50 mg IV (or oral equivalent) diphenhydramine, and 650 mg IV (or oral equivalent) acetaminophen/paracetamol (per local practice) is mandatory and should be administered approximately 30 to 60 minutes prior to each dose of avelumab. This may be modified, as appropriate, according to local treatment practice and guidelines.

If the avelumab is administered more than 1 hour after the preceding drug and/or if no premedication has already been administered, then the premedication must be repeated and/or initiated. The line should be flushed, according to local practice, between infusions, and a new administration set should be used for avelumab.

Avelumab should be administered in a setting that allows for immediate access to an intensive care unit or equivalent environment and administration of therapy for anaphylaxis, such as the ability to implement immediate resuscitation measures. Steroids (dexamethasone 10 mg), epinephrine (1: 1,000 dilution), allergy medications (IV antihistamines), bronchodilators or equivalents and oxygen should be available for immediate access. Infusion of avelumab will be stopped in case of Grade ≥ 2 infusion-related, allergic, or anaphylactic reactions. Following avelumab infusion, patients must be observed for 2 hours for potential infusion-related reactions. If an allergic reaction occurs, the patient should be treated according to the best available medical practice. Patients should be instructed to report any delayed reactions to the Investigator immediately. Monitoring may be reduced to 30 minutes after cycle 1 at the investigator's discretion.

Investigators should additionally monitor patients closely for potential irAEs, which may only become apparent following several weeks of treatment. Immune-related adverse events described with this class of drugs include pneumonitis, colitis, hepatitis, endocrinopathies including thyroid disorders (hyperthyroidism, hypothyroidism, thyroiditis), adrenal insufficiency, hypophysitis, and diabetes mellitus, renal dysfunction, encephalitis, eye disorders (uveitis, iritis), myositis and myocarditis. Treatment recommendations for the management of irAEs are

outlined in Section 6.3 and Table 2.

6.2 Management of Avelumab Infusion-Related Reactions

Symptoms may include one or more of the following: fever, chills, rigors, diaphoresis, and headache.

Once the avelumab infusion rate has been decreased by 50% due to an infusion-related reaction, the same decreased infusion rate must be used for all subsequent infusions.

Table 1. Avelumab Treatment Modifications for Symptoms of Infusion Related Reactions

NCI-CTCAE Grade	Treatment Modification for Avelumab
Grade 1 – mild	
 Mild transient reaction; infusion interruption not indicated; intervention not indicated 	 Decrease the avelumab infusion rate by 50% and monitor closely for any worsening
 Grade 2 – moderate Therapy or infusion interruption indicated but 	 Temporarily discontinue avelumab infusion
responds promptly to symptomatic treatment (for example, antihistamines, NSAIDs, narcotics, IV fluids); prophylactic medications indicated for ≤ 24h	 Resume infusion at 50% of previous rate once infusion-related reaction has resolved or decreased to at least Grade 1 in severity, and monitor closely for any worsening
Grade 3 or Grade 4 – severe or life-threatening	
 Grade 3: Prolonged (for example, not rapidly responsive to symptomatic medication and/or brief interruption of infusion); recurrence of symptoms following initial improvement; hospitalization indicated for clinical sequelae Grade 4: Life-threatening consequences; urgent intervention indicated 	 Stop the avelumab infusion immediately and disconnect infusion tubing from the subject Subjects have to be withdrawn immediately from avelumab treatment and must not receive any further avelumab treatment

IV: intravenous; NCI-CTCAE: National Cancer Institute-Common Terminology Criteria for Adverse Event; NSAIDs: nonsteroidal anti-inflammatory drugs.

6.2.1 Additional Avelumab Treatment Modifications for Patients with Grade 2 Infusion- Related Reactions

In the event of a Grade 2 infusion-related reaction that does not improve or that worsens following implementation of the modifications indicated in Table 1 (including reducing the infusion rate by 50%), the Investigator may consider treatment with corticosteroids per local guidelines, and the infusion should be stopped for that day. At the time of the next cycle, the Investigator may consider adding H2-blocker antihistamines (eg, famotidine or ranitidine) and/or hydrocortisone 100mg IV, or the steroid equivalent, to the mandatory pre-medication.

If the patient has a second infusion-related reaction of Grade ≥ 2 on the reduced infusion rate, with or without the addition of further medication/s to the mandatory pre-medication, the infusion should be stopped, and the patient discontinued from avelumab treatment.

6.2.2 Management of Avelumab Severe Hypersensitivity Reactions and Flu-Like Symptoms

Symptoms of hypersensitivity may include impaired airway, decreased oxygen saturation (<92%), confusion, lethargy, hypotension, pale or clammy skin, and cyanosis. These symptoms may, if necessary, be managed with epinephrine and dexamethasone. Oxygen therapy should be administered as appropriate. Patients should be immediately placed on a cardiac monitor, and the intensive care unit (ICU) alerted for possible transfer if required. In extreme cases, intubation may be necessary.

For prophylaxis of flu-like symptoms, 25 mg of indomethacin or a comparable nonsteroidal anti-inflammatory drug (NSAID) dose (for example, ibuprofen 600 mg, naproxen sodium 500 mg) may be administered 2 hours prior to and 8 hours after the start of each avelumab IV infusion. Alternative treatments for fever (eg, paracetamol) may be given to patients at the discretion of the Investigator.

6.3 Immune-Related Adverse Events

NOTE: The same irAE management guidelines apply to utomilumab, avelumab and PF-04518600.

As these drugs stimulate the immune system, irAEs may occur. Treatment of irAEs is dependent upon their severity (NCI-CTCAE grade):

•	Grade 1 to 2:	treat symptomatically or with moderate dose steroids, and more frequent monitoring;
•	Grade 1 to 2 (persistent):	manage as per high-grade (ie, Grade 3 to 4) AEs;
•	Grade 3 to 4:	treat with high-dose corticosteroids.

Any event suspected to be immune-related should be managed according to the guidance for management of immune-related adverse events in this section and in Table 2. There are no dose modifications on this protocol of any of the agents. However, treatment may be temporarily or permanently discontinued following the recommendations in Table 2. Also note that the recommendations may be superseded by the judgement of the treating clinician, although this should be discussed with the Study Chair.

Immune-related adverse events described with this class of drugs include: pneumonitis, colitis, hepatitis, endocrinopathies including thyroid disorders (hyperthyroidism, hypothyroidism, thyroiditis), adrenal insufficiency, hypophysitis, and diabetes mellitus or hyperglycemia, rash, nephritis and renal dysfunction, encephalitis, eye disorders (including uveitis, iritis), and other immune-mediated reactions including myositis and myocarditis.

Any adverse event which may have an underlying immune-mediated mechanism including those described above, and without other confirmed etiologies, should be considered immune-related and managed according to guidelines described in this section.

Gastrointestinal irAEs			
Severity of Diarrhea/Colitis (NCI-CTCAE v4)	Initial Management	Follow-up Management	
Grade 1 Diarrhea: < 4 stools/day over Baseline Colitis: asymptomatic	Continue immunotherapy agent Symptomatic treatment (e.g. loperamide)	Close monitoring for worsening symptoms Educate subject to report worsening immediately If worsens: Treat as Grade 2, 3 or 4.	
Grade 2 Diarrhea: 4 to 6 stools per day over Baseline; IV fluids indicated < 24 hours; not interfering with ADL Colitis: abdominal pain; blood in stool	Withhold all immunotherapy agents Symptomatic treatment	If improves to Grade ≤ 1: Resume immunotherapy agents If persists > 5-7 days or recurs: Treat as Grade 3 or 4.	
Grade 3 to 4 Diarrhea (Grade 3): ≥ 7 stools per day over Baseline; incontinence; IV fluids ≥ 24 h; interfering with ADL Colitis (Grade 3): severe abdominal pain, medical intervention indicated, peritoneal signs Grade 4: life-threatening, perforation	Withhold all immunotherapy agents for Grade 3. Permanently discontinue immunotherapy agents for Grade 4 or recurrent Grade 3. 1.0 to 2.0 mg/kg/day prednisone IV or equivalent Add prophylactic antibiotics for opportunistic infections Consider lower endoscopy	If improves: Continue steroids until Grade ≤ 1, then taper over at least 1 month; resume immunotherapy agents following steroids taper (for initial Grade 3). If worsens, persists > 3 to 5 days, or recurs after improvement: Add infliximab 5mg/kg (if no contraindication). Note: infliximab should not be used in cases of perforation or sepsis.	
	Dermatological irAEs		
Grade of Rash (NCI-CTCAE v4)	Initial Management	Follow-up Management	
Grade 1 to 2 Covering ≤ 30% body surface area	Continue immunotherapy agents Symptomatic therapy (for example, antihistamines, topical steroids)	If persists > 1 to 2 weeks or recurs: Withhold all immunotherapy agents Consider skin biopsy Consider 0.5-1.0 mg/kg/day prednisone or equivalent. Once improving, taper steroids over at least 1 month, consider prophylactic antibiotics for opportunistic infections, and resume immunotherapy agents following steroids taper. If worsens:	

Table 2. Management of Immune Related Adverse Events

Treat as Grade 3 to 4.

Grade 3 to 4 Grade 3: Covering > 30% body surface area; Grade 4: Life threatening	Withhold all immunotherapy agents for Grade 3. Permanently discontinue for Grade 4 or recurrent Grade 3.	If improves to Grade ≤ 1: Taper steroids over at least 1 month; resume immunotherapy agents following steroids taper (for initial Grade 3).
consequences	Consider skin biopsy Dermatology consult 1.0 to 2.0 mg/kg/day prednisone or equivalent Add prophylactic antibiotics for opportunistic infections	
	Pulmonary irAEs	
Grade of Pneumonitis (NCI-CTCAE v4)	Initial Management	Follow-up Management
Grade 1 Radiographic changes only	Consider withholding all immunotherapy agents Monitor for symptoms every 2 to 3 days Consider Pulmonary and Infectious Disease consults	Re-assess at least every 3 weeks If worsens: Treat as Grade 2 or Grade 3 to 4.
Grade 2 Mild to moderate new symptoms	Withhold all immunotherapy agents Pulmonary and Infectious Disease consults Monitor symptoms daily; consider hospitalization 1.0 to 2.0 mg/kg/day prednisone or equivalent Add prophylactic antibiotics for opportunistic infections Consider bronchoscopy, lung biopsy	Re-assess every 1 to 3 days If improves: When symptoms return to Grade ≤ 1, taper steroids over at least 1 month, and then resume all immunotherapy agents following steroids taper If not improving after 2 weeks or worsening: Treat as Grade 3 to 4.
Grade 3 to 4 Grade 3: Severe new symptoms; New/worsening hypoxia; Grade 4: Life-threatening	Permanently discontinue all immunotherapy agents. Hospitalize. Pulmonary and Infectious Disease consults. 1.0 to 2.0 mg/kg/day prednisone or equivalent Add prophylactic antibiotics for opportunistic infections Consider bronchoscopy, lung biopsy	If improves to Grade ≤ 1: Taper steroids over at least 1 month If not improving after 48 hours or worsening: Add additional immunosuppression (for example, infliximab, cyclophosphamide, IV immunoglobulin, or mycophenolate mofetil)
	Hepatic irAEs	
Grade of Liver Test Elevation (NCI-CTCAE v4)	Initial Management	Follow-up Management
Grade 1	Continue immunotherapy agents	Continue liver function monitoring If worsens:

Grade 1 AST or ALT > ULN to 3.0 x ULN and/or Total bilirubin > ULN to 1.5 x ULN		Treat a	as Grade 2 or 3 to 4.
Grade 2 AST or ALT > 3.0 to $\leq 5 \times ULN$ and/or total bilirubin > 1.5 to $\leq 3 \times ULN$	Withhold all immunotherapy agents Increase frequency of monitoring to every 3 days.	Resum immuno If eleva	ns to Grade ≤ 1: e routine monitoring; resume otherapy agents. tion persists > 5 to 7 days or worsens: s Grade 3 to 4.
Grade 3 to 4 AST or ALT > 5 x ULN and/or total bilirubin > 3 x ULN	Permanently discontinue all immunotherapy agents Increase frequency of monitoring to every 1 to 2 days 1.0 to 2.0 mg/kg/day prednisone or equivalent Add prophylactic antibiotics for opportunistic infections Consult gastroenterologist/ hepatologist Consider obtaining MRI/CT scan of liver and liver biopsy if clinically warranted	Taper s If does or rebo Add my daily If no re days, c	ns to Grade ≤ 1: steroids over at least 1 month not improve in > 3 to 5 days, worsens unds: vcophenolate mofetil 1 gram (g) twice sponse within an additional 3 to 5 onsider other immunosuppressants al guidelines.
	Renal irAEs l		
Grade of Creatinine Increased (NCI-CTCAE v4)	Initial Management		
	initial management		Follow-up Management
Grade 1 Creatinine increased > ULN to 1.5 x ULN	Continue immunotherapy agent	ts	Follow-up Management Continue renal function monitoring If worsens: Treat as Grade 2 to 3 or 4.
Creatinine increased > ULN to 1.5 x		ents ng to e or	Continue renal function monitoring If worsens:
+For pts with a baseline Cr 1-1.5x ULN, management of specific changes in Cr are at the discretion of the treating physician

	Cardiac irAEs	
Myocarditis	Initial Management	Follow-up Management
New onset of cardiac signs or symptoms and / or new laboratory cardiac biomarker elevations (e.g. troponin, CK-MB, BNP) or cardiac imaging abnormalities suggestive of myocarditis.	 Withhold all immunotherapy agents. Hospitalize. In the presence of life threatening cardiac decompensation, consider transfer to a facility experienced in advanced heart failure and arrhythmia management. Cardiology consult to establish etiology and rule-out immune-mediated myocarditis. Guideline based supportive treatment as per cardiology consult. * Consider myocardial biopsy if recommended per cardiology consult. 	If symptoms improve and immune-mediated etiology is ruled out, re-start immunotherapy agents. If symptoms do not improve/worsen, viral myocarditis is excluded, and immune-mediated etiology is suspected or confirmed following cardiology consult, manage as immune-mediated myocarditis.
Immune-mediated myocarditis	Permanently discontinue all immunotherapy agents. Guideline based supportive treatment as appropriate as per cardiology consult. * 1.0 to 2.0 mg/kg/day prednisone or equivalent Add prophylactic antibiotics for opportunistic infections.	Once improving, taper steroids over at least 1 month. If no improvement or worsening, consider additional immunosuppressants (e.g. azathioprine, cyclosporine A).

ESC guidelines website: https://www.escardio.org/Guidelines/Clinical-Practice-Guidelines

AHA guidelines website:

http://professional.heart.org/professional/GuidelinesStatements/searchresults.jsp?q=&y=&t=1001

Endocrine irAEs

		-
Endocrine Disorder	Initial Management	Follow-up Management
Grade 1 or Grade 2 endocrinopathies (hypothyroidism, hyperthyroidism, adrenal insufficiency, type I diabetes mellitus)	Continue immunotherapy agents Endocrinology consult if needed Start thyroid hormone replacement therapy (for hypothyroidism), anti-thyroid treatment (for hyperthyroidism), corticosteroids (for adrenal insufficiency) or insulin (for Type I diabetes mellitus) as appropriate. Rule-out secondary endocrinopathies (i.e. hypopituitarism / hypophysitis)	Continue hormone replacement/suppression and monitoring of endocrine function as appropriate.

Grade 3 or Grade 4	Withhold all immunetherapy agents	Pooumo all immunotherany agente
endocrinopathies (hypothyroidism, hyperthyroidism, adrenal insufficiency, type I diabetes mellitus)	Withhold all immunotherapy agents Consider hospitalization Endocrinology consult Start thyroid hormone replacement therapy (for hypothyroidism), anti-thyroid treatment (for hyperthyroidism), corticosteroids (for adrenal insufficiency) or insulin (for type I diabetes mellitus) as appropriate. Rule-out secondary endocrinopathies	Resume all immunotherapy agents once symptoms and/or laboratory tests improve to Grade ≤ 1 (with or without hormone replacement/suppression). Continue hormone replacement/suppression and monitoring of endocrine function as appropriate.
Hypopituitarism/Hypophysitis (secondary endocrinopathies)	 (i.e. hypopituitarism / hypophysitis) If secondary thyroid and/or adrenal insufficiency is confirmed (i.e. subnormal serum FT4 with inappropriately low TSH and/or low serum cortisol with inappropriately low ACTH) : Refer to endocrinologist for dynamic testing as indicated and measurement of other hormones (FSH, LH, GH/IGF- 1, PRL, testosterone in men, estrogens in women) Hormone replacement/suppressive therapy as appropriate Perform pituitary MRI and visual field examination as indicated If hypophysitis confirmed: Continue all immunotherapy agents if mild symptoms with normal MRI. Repeat the MRI in 1 month Withhold all immunotherapy agents if moderate, severe or life- threatening symptoms of hypophysitis and/or abnormal MRI. Consider hospitalization. Initiate corticosteroids (1 to 2 mg/kg/day prednisone or equivalent) followed by corticosteroids taper during at least 1 month. Add prophylactic antibiotics for opportunistic infections. 	Resume all immunotherapy agents once symptoms and hormone tests improve to Grade ≤ 1 (with or without hormone replacement). In addition, for hypophysitis with abnormal MRI, resume avelumab only once shrinkage of the pituitary gland on MRI/CT scan is documented. Continue hormone replacement/suppression therapy as appropriate.
	Other irAEs (not described above)	
Grade of other irAEs (NCI-CTCAE v4)	Initial Management	Follow-up Management

Grade 2 or Grade 3 clinical signs or symptoms suggestive of a potential irAE	Withhold all immunotherapy agents pending clinical investigation	If irAE is ruled out, manage as appropriate according to the diagnosis and consider re-starting all immunotherapy agents If irAE is confirmed, treat as Grade 2 or 3 irAE.
Grade 2 irAE or first occurrence of Grade 3 irAE	Withhold all immunotherapy agents 1.0 to 2.0 mg/kg/day prednisone or equivalent Add prophylactic antibiotics for opportunistic infections Specialty consult as appropriate	If improves to Grade ≤ 1: Taper steroids over at least 1 month and resume all immunotherapy agents following steroids taper.
Recurrence of same Grade 3 irAEs	Permanently discontinue all immunotherapy agents 1.0 to 2.0 mg/kg/day prednisone or equivalent Add prophylactic antibiotics for opportunistic infections Specialty consult as appropriate	If improves to Grade ≤ 1: Taper steroids over at least 1 month.
Grade 4	Permanently discontinue all immunotherapy agents 1.0 to 2.0 mg/kg/day prednisone or equivalent and/or other immunosuppressant as needed Add prophylactic antibiotics for opportunistic infections Specialty consult.	If improves to Grade ≤ 1: Taper steroids over at least 1 month
Requirement for 10 mg per day or greater prednisone or equivalent for more than 12 weeks for reasons other than hormonal replacement for adrenal insufficiency	Permanently discontinue all immunotherapy agents Specialty consult	
Persistent Grade 2 or 3 irAE lasting 12 weeks or longer		

6.4 **Recommended Treatment Modifications**

Dose delays for drug-related non-immune related toxicities related to utomilumab, avelumab, PF-04518600, and rituximab are detailed in Table 3 and Table 4. If a toxicity can be attributed just to one of the drugs in the combination, dose delays can be implemented independently for each drug. In instances where it is not possible to attribute the toxicity to only one of the three drugs, the treatment modifications detailed in Table 3 and Table 4 should be followed for all drugs.

Hematologic Toxicity (NCI	Utomilumab	Avelumab	PF-04518600	Rituximab
CTCAE				
version 4.03)				
Grade 1	Continue per schedule	Continue per	Continue per	Continue per
	1	schedule	schedule	schedule
Grade 2	Continue per schedule	Continue per	Continue per	Continue per
	1	schedule	schedule	schedule
Grade 3	Hold treatment up to 4 weeks until Grade_≤1, or baseline then rechallenge.	Hold treatment up to 4 weeks until Grade ≤1, or baseline, then rechallenge.	Hold treatment up to 4 weeks until Grade ≤1, or baseline, then rechallenge.	Hold treatment up to 4 weeks until Grade ≤1, or baseline, then rechallenge.
	Permanent discontinuation if recurrence to Grade 3 (Unless resolve to Grade ≤1 or baseline within 7 days following appropriate medical management).	Permanent discontinuation if recurrence to Grade 3. (Unless resolve to Grade ≤ 1 or baseline within 7 days following appropriate medical management	Permanent discontinuation if recurrence to Grade 3. (Unless resolve to Grade ≤ 1 or baseline within 7 days following appropriate medical management	Permanent discontinuation if recurrence to Grade 3. (Unless resolve to Grade ≤ 1 or baseline within 7 days following appropriate medical management

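### Section 6.3 sends every persistent Grade 1-2 immune event to Grade 3-4 management, but Table 2 gives a different action for Grade 1 gut, liver, kidney and lung events and for Grade 1-2 endocrinopathy and rash

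*Combined protocol and SAP*

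**What the plan says.** Section 6.3 opens with three treatment rules by severity. Low-grade events receive symptomatic care or steroids at a moderate dose, with closer follow-up. When such an event persists, the instruction becomes "manage as per high-grade (ie, Grade 3 to 4) AEs". What that upper band entails is set by the last of the three rules, under which the site is told to "treat with high-dose corticosteroids".

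The list does not say how long an event must last to count as persistent, and it exempts no organ. Section 6.3 then states that any suspected immune-related event "should be managed according to the guidance for management of immune-related adverse events in this section and in Table 2". It gives no order of precedence between the two.

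Table 2, in the same section, sets actions organ by organ. For a Grade 1 liver test elevation the drugs continue and the follow-up entry reads "Continue liver function monitoring If worsens", after which a higher grade's management applies. For Grade 3 to 4 liver events it reads "Permanently discontinue all immunotherapy agents Increase frequency of monitoring to every 1 to 2 days", together with prednisone 1.0 to 2.0 mg/kg/day. For Grade 1 or 2 endocrinopathies it reads "Continue immunotherapy agents Endocrinology consult if needed", with hormone replacement or suppression as needed.

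**The concern.** The two texts give different instructions for the same patient, and both are declared applicable. A site working from the severity list and a site working from Table 2 could each be following the protocol while one continues all agents and the other starts high-dose steroids and, in some organs, stops treatment for good.

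This touches what the trial reports. Adverse events leading to discontinuation for toxicity are a secondary safety endpoint in Section 13.1, and each expanded cohort is only 15 patients. Steroid exposure also matters to the sponsor: Section 5.3.6 warns that immunosuppressives may work against the study treatment, although it adds that short-term steroid use with another class of immunotherapy has not been found to compromise outcome. If the two instructions are applied unevenly across sites, part of any difference in exposure or discontinuation will reflect which text was read.

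**Working it through.** No arithmetic applies. The check sets the Section 6.3 rule for persistent Grade 1-2 events against each legible organ-specific Grade 1 or Grade 2 row of Table 2.

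| Table 2 row | What Table 2 does if the event persists | Against the 6.3 bullet |
|---|---|---|
| Gastrointestinal, Grade 1 | Drug continues; escalates only on worsening | Conflict |
| Hepatic, Grade 1 | Drug continues; escalates only on worsening | Conflict |
| Renal, Grade 1 | Drug continues; escalates only on worsening | Conflict |
| Endocrine, Grade 1-2 | Drug continues with hormone treatment; no persistence trigger | Conflict |
| Pneumonitis, Grade 1 | Withholding is optional; escalates only on worsening | Conflict, weaker |
| Rash, Grade 1-2 | Past 1 to 2 weeks: withhold, consider 0.5-1.0 mg/kg/day, resume after taper; Grade 3-4 management only on worsening | Conflict of a different kind |
| Gastrointestinal, Grade 2 | Withheld; past 5-7 days, treated as Grade 3 or 4 | Agrees |
| Hepatic, Grade 2 | Withheld; past 5 to 7 days, treated as Grade 3 to 4 | Agrees |
| Pneumonitis, Grade 2 | Withheld with steroids; no improvement after 2 weeks, treated as Grade 3 to 4 | Agrees |

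Six rows conflict and three agree. The higher-grade renal rows are broken in the text available for this review and were not scored.

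The next step is to follow the Section 6.3 bullet into the Grade 3-4 row for each conflicting organ:

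- **Hepatic and pneumonitis.** The Grade 3-4 row requires permanent discontinuation plus prednisone 1.0 to 2.0 mg/kg/day. A persistent Grade 1 liver elevation therefore moves from continued drug to permanent stopping.
- **Gastrointestinal and rash.** The row withholds for a first Grade 3 event and allows resumption after the steroid taper. Permanent stopping is reserved for Grade 4 or recurrent Grade 3.
- **Endocrine.** The row withholds and resumes at Grade 1 or lower, with or without hormone treatment. It contains no general high-dose steroid course; that comes only from the Section 6.3 list.

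Finally, *persistent* has no single meaning. Table 2 uses more than 5-7 days for Grade 2 gut and liver events, more than 1 to 2 weeks for rash, 2 weeks without improvement for Grade 2 pneumonitis, and a separate 12-week limit for Grade 2 or 3 events in its last block. Section 6.3 gives none.

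**The case against.** The best defence is that Table 2 is plainly the working document. The introduction to Section 6 sends suspected immune events to Table 2. Section 6.7 cites Section 6.3 and then directs management to Table 2. Section 5.3.6 permits steroids for these events as Table 2 sets out. Section 6.3 itself ties temporary or permanent discontinuation to Table 2. On this view the three bullets are a general preface containing no stopping rule. Section 6.3 also allows the treating clinician's judgement to override the recommendations, with discussion with the Study Chair.

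Much of this is fair, and it lowers the chance that sites diverge. It does not remove the contradiction. None of those sentences says that Table 2 prevails, and Section 6.7 names the Section 6.3 guidelines as applying too. Tying discontinuation to Table 2 does not help when the bullet directs the reader to Table 2's Grade 3-4 rows. The override is case by case, and the introduction to Section 6 makes the modification recommendations binding unless departure has been agreed beforehand with the Principal Investigator.

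A reader might also infer a conflict in the opposite direction, because the list gives Grade 2 events symptomatic or moderate-dose treatment while Table 2's row for "Grade 2 irAE or first occurrence of Grade 3 irAE" in other organs gives 1.0 to 2.0 mg/kg/day. The documents do not carry that: Section 6.3 attaches no mg/kg figure to a moderate or a high dose, so the two cannot be shown to differ.

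**Conclusion.** The contradiction is real and is wrong as written. It covers Grade 1 gastrointestinal, hepatic, renal and lung events and Grade 1-2 endocrinopathy and rash, when any of these persists. It is most serious for Grade 1 hepatic and lung events, where the literal reading ends in mandatory permanent discontinuation.

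Three larger conclusions might be drawn and are not supported:

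- *That Table 2 continues drug for all persistent low-grade events.* It does not: persistent Grade 2 gut, liver and lung events are withheld and escalated in line with Section 6.3, and persistent rash is withheld.
- *That the bullet leads to permanent stopping in every organ.* It does not for endocrine events, or for first Grade 3 gut events or rash.
- *That the affected number can be read from the listed event rates*, such as AST increase of 21.2% and ALT increase of 15.4% in Section 8.1.4.4. Those are all-grade rates regardless of causality, from patients with advanced solid tumours across doses of 0.01 to 10 mg/kg. The share that is immune-related, low grade and persistent is not given.

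Nor is any effect shown on the response or toxicity decisions. Dose-limiting toxicities are defined in Section 5.1 mainly from Grade 3 upward, and nothing in the documents links this conflict to the count of complete responses. The conclusion rests on reading Section 6.3 literally and on the absence of any precedence statement.

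**What to change.** Reconcile the persistent-event bullet in Section 6.3 with the six Table 2 rows, so that each combination of organ, grade and persistence has one action for study drug and one for steroids. Make the meaning of *persistent* consistent between the list and the table, with any organ-specific durations shown as such. State in Section 6.3 which text governs where they differ. Which action applies is a clinical decision for the sponsor's clinicians, and this review takes no position on it. The cost is a wording amendment to Section 6.3, Table 2 or both, and notice of it to sites; it needs no extra patients, visits or procedures.
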